10.1.9 Source Documents

Source documents provide evidence for the existence of the participant and substantiate the integrity of the data collected. The investigator/institution should maintain adequate and accurate source documents and study records that include all pertinent observations on each of the site's participants. Source documents and data should be attributable, legible, contemporaneous, original, accurate, and complete. Changes to source data should be traceable, should not obscure the original entry, and should be explained if necessary (eg, via an audit trail). Source documents are filed at the investigator's site.

Data reported on the CRF or entered in the eCRF that are transcribed from source documents must be consistent with the source documents or the discrepancies must be explained. The investigator/institution may need to request previous medical records or transfer records, depending on the study. Also, current medical records must be available.

10.1.10 Study and Site Closure

The Sponsor or its designee may stop the study or study-site participation in the study for medical, safety, regulatory, administrative, or other reasons consistent with applicable laws, regulations, and GCP.

In the event the Sponsor prematurely terminates a particular study site, the Sponsor or designee will promptly notify that study site's IRB/IEC as specified by applicable regulatory requirement(s).

10.2 Appendix 2: Clinical Laboratory Tests

- The tests detailed in [Table 15](#) will be performed by the local laboratory.
- Protocol-specific requirements for inclusion or exclusion of participants are detailed in Section 5 of the protocol.
- Additional tests may be performed at any time during the study as determined necessary by the investigator or required by local regulations. See country-specific requirements in Appendix 7.

Table 15 Protocol-required Safety Laboratory Assessments

Laboratory Assessments	Parameters			
Hematology	Platelet Count	RBC Indices ^a : MCV MCH % Reticulocytes		WBC count with Differential ^b : Neutrophils Lymphocytes Monocytes Eosinophils Basophils
	RBC Count			
	Hemoglobin			
	Hematocrit			
Chemistry	BUN ^c	Potassium	AST/SGOT	Total bilirubin (and direct bilirubin, if total bilirubin is above the ULN)
	Albumin	Carbon dioxide (CO ₂ or Bicarbonate)	Chloride	Phosphorous
	Creatinine ^d	Sodium	ALT/SGPT	Total Protein
	Glucose (fasting preferred)	Calcium	Alkaline phosphatase	Amylase/Lipase ^e
Routine Urinalysis ^f	
 Specific gravity pH, glucose, protein, blood, ketones by dipstick Microscopic examination (if blood or protein is abnormal) 			
Pregnancy Testing ^g	
 Highly sensitive serum or urine pregnancy test (as needed for WOCBP) 			
Screening Only Tests	
 PT/INR and aPTT/PTT^h FSH (as needed in WONCBP only)ⁱ Serology (HIV antibody, HBsAg, and Hepatitis C virus antibody). NOTE: certain ex-US sites require testing for HIV and Hepatitis B and C during screening. Consult with regional health authorities and institutional standards to confirm if such testing is applicable.^j 			

Laboratory Assessments	Parameters
Other Tests	
 • Thyroid function test: TSH, T3/T4, and free T3/T4^k • Cortisol (collect specimens at the same time of day) and ACTH (ACTH testing is to be done per investigator's discretion) • Serum Tumor Marker (CEA)

ACTH=adrenocorticotrophic hormone; ALT=alanine aminotransferase; aPTT= activated partial thromboplastin time; AST=aspartate aminotransferase; BUN=blood urea nitrogen; C1D1=Cycle 1 Day 1; CEA= carcinoembryonic antigen; DNA= deoxyribonucleic acid; FSH=follicle-stimulating hormone; hCG=human chorionic gonadotropin; HBsAg= Hepatitis B surface antigen; HBV=Hepatitis B Virus; HCV=Hepatitis C Virus; INR= international normalized ratio; MCH=mean corpuscular hemoglobin; MCV=mean corpuscular volume; PT=prothrombin time; PTT= partial thromboplastin time; RBC=red blood cell; RNA= ribonucleic acid; SGOT=serum glutamic oxaloacetic transaminase; SGPT=serum glutamic pyruvic transaminase; T3/T4= triiodothyronine/ thyroxine; TSH=thyroid-stimulating hormone; ULN=upper limit of normal; WOCBP=women of childbearing potential; WONCBP=women of nonchildbearing potential.
 
a. Performed only if considered local standard of care.
 
b. Absolute or % acceptable per institutional standard.
 
c. Urea is acceptable if BUN is not available as per institutional standard.
 
d. Glomerular filtration rate (GFR) (measured or calculated) or creatinine clearance can be used in place of creatinine.
 
e. Obtain lipase and amylase at screening, EOT and 30-day follow-up.
 
f. If urine dipstick is abnormal, urinalysis must be performed.
 
g. Perform on WOCBP only 24 hours before first dose. Pregnancy tests must be repeated before every cycle.
 
h. Performed as part of the screening assessment for all participants and as clinically indicated for participants taking anticoagulants.
 
i. If necessary, to check menopausal status.
 
j. HBsAg or HBV DNA. HCV RNA (qualitative) or HCV antibody.
 
k. Participants may be dosed while thyroid function tests are pending. Free T3/T4 is acceptable when total T3/T4 cannot be determined.
	

The investigator (or medically qualified designee) must document their review of each laboratory safety report.

10.3 Appendix 3: Adverse Events: Definitions and Procedures for Recording, Evaluating, Follow-up, and Reporting

10.3.1 Definitions of Medication Error, Misuse, and Abuse

Medication error

This is an unintended failure in the drug treatment process that leads to or has the potential to lead to harm to the patient.

Misuse

This refers to situations where the medicinal product is intentionally and inappropriately used not in accordance with the terms of the product information.

Abuse

This corresponds to the persistent or sporadic intentional, excessive use of a medicinal product for a perceived psychological or physiological reward or desired nontherapeutic effect.

10.3.2 Definition of AE

AE definition

[figure not shown]
- An AE is any untoward medical occurrence in a clinical study participant, temporally associated with the use of study intervention, whether or not considered related to the study intervention.
- Note: An AE can therefore be any unfavorable and unintended sign (including an abnormal laboratory finding), symptom, or disease (new or exacerbated) temporally associated with the use of a study intervention.
- Note: For purposes of AE definition, study intervention includes any pharmaceutical product, biological product, vaccine, diagnostic agent, medical device, combination product, or protocol-specified procedure whether investigational or marketed (including placebo, active comparator product, or run-in intervention), manufactured by, licensed by, provided by, or distributed by the Sponsor for human use in this study.

Events meeting the AE definition

- Any abnormal laboratory test results (hematology, clinical chemistry, or urinalysis) or other safety assessments (eg, ECG, radiological scans, vital signs measurements), including those that worsen from baseline, considered clinically significant in the medical and scientific judgment of the investigator.
- Exacerbation of a chronic or intermittent preexisting condition including either an increase in frequency and/or intensity of the condition.

- New conditions detected or diagnosed after study intervention administration even though it may have been present before the start of the study.
- Signs, symptoms, or the clinical sequelae of a suspected drug-drug interaction.
- Signs, symptoms, or the clinical sequelae of a suspected overdose of either study intervention or a concomitant medication.
- For all reports of overdose (whether accidental or intentional) with an associated AE, the AE term should reflect the clinical symptoms or abnormal test result. An overdose without any associated clinical symptoms or abnormal laboratory results is reported using the terminology “accidental or intentional overdose without adverse effect.”
- Any new cancer (that is not a condition of the study). Progression of the cancer under study is not considered a reportable event unless it results in hospitalization or death. Refer to Section 8.4.6 for additional details.

Events NOT meeting the AE definition

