8.4 Adverse Events, Serious Adverse Events, and Other Reportable Safety Events

The definitions of an AE or SAE, as well as the method of recording, evaluating, and assessing causality of AE and SAE and the procedures for completing and transmitting AE, SAE, and other reportable safety event reports can be found in Appendix 3.

Progression of the cancer under study is not considered an AE as described in Section 8.4.6 and Appendix 3.

Adverse events, SAEs, and other reportable safety events will be reported by the participant (or, when appropriate, by a caregiver, surrogate, or the participant's legally authorized representative).

The investigator and any designees are responsible for detecting, documenting, and reporting events that meet the definition of an AE or SAE as well as other reportable safety events. Investigators need to document if an SAE was associated with a medication error, misuse, or abuse.

Investigators remain responsible for following up AEs, SAEs, and other reportable safety events for outcome according to Section 8.4.3. The investigator, who is a qualified physician, will assess events that meet the definition of an AE or SAE as well as other reportable safety events with respect to seriousness, intensity/toxicity, and causality.

8.4.1 Time Period and Frequency for Collecting AE, SAE, and Other Reportable Safety Event Information

All AEs, SAEs, and other reportable safety events that occur after the participant provides documented informed consent, but before intervention allocation, must be reported by the investigator if the participant is receiving placebo run-in or other run-in treatment, if the event causes the participant to be excluded from the study, or is the result of a protocol-specified intervention, including, but not limited to washout or discontinuation of usual therapy, diet, or a procedure.

- All AEs from the time of intervention allocation through 30 days after cessation of study intervention must be reported by the investigator.
- All AEs meeting serious criteria, from the time of intervention allocation through 90 days after cessation of study intervention or 30 days after cessation of study intervention if the participant initiates new anticancer therapy, whichever is earlier, must be reported by the investigator.

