8.4.6 Disease-related Events and/or Disease-related Outcomes Not Qualifying as AEs or SAEs

Efficacy endpoints as outlined in this section will not be reported to the Sponsor as described in Section 8.4.1.

Specifically, the suspected/actual events covered in this exception include any event that is disease progression of the cancer under study.

The Sponsor will ensure that unblinded aggregated efficacy endpoint events and safety data are monitored to safeguard the participants in the study. Any suspected endpoint that upon review is not progression of the cancer under study will be forwarded to Global Pharmacovigilance as an SAE within 24 hours of determination that the event is not progression of the cancer under study.

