9.4.2 Safety Endpoints

Safety and tolerability will be assessed by clinical review of all relevant parameters, including AEs, SAEs, fatal AEs, laboratory tests, and vital signs. Furthermore, specific events will be collected and designated as ECIs as described in Section 8.4.7.

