10.3.3 Definition of SAE

If an event is not an AE per definition above, then it cannot be an SAE even if serious conditions are met.

An SAE is defined as any untoward medical occurrence that, at any dose:

- a. Results in death
- b. Is life-threatening
 - The term “life-threatening” in the definition of “serious” refers to an event in which the participant was at risk of death at the time of the event. It does not refer to an event, which hypothetically might have caused death, if it were more severe.
- c. Requires inpatient hospitalization or prolongation of existing hospitalization
 - Hospitalization is defined as an inpatient admission, regardless of length of stay, even if the hospitalization is a precautionary measure for continued observation. (Note: Hospitalization for an elective procedure to treat a preexisting condition that has not

worsened is not an SAE.) A preexisting condition is a clinical condition that is diagnosed prior to the use of an MSD product and is documented in the participant's medical history.

- d. Results in persistent or significant disability/incapacity
 - The term disability means a substantial disruption of a person's ability to conduct normal life functions.
 - This definition is not intended to include experiences of relatively minor medical significance such as uncomplicated headache, nausea, vomiting, diarrhea, influenza, and accidental trauma (eg, sprained ankle) that may interfere with or prevent everyday life functions but do not constitute a substantial disruption.
- e. Is a congenital anomaly/birth defect
 - In offspring of participant taking the product regardless of time to diagnosis.
- f. Other important medical events
 - Medical or scientific judgment should be exercised in deciding whether SAE reporting is appropriate in other situations such as important medical events that may not be immediately life-threatening or result in death or hospitalization but may jeopardize the participant or may require medical or surgical intervention to prevent 1 of the other outcomes listed in the above definition. These events should usually be considered serious.
 - Examples of such events include invasive or malignant cancers, intensive treatment in an emergency room or at home for allergic bronchospasm, blood dyscrasias, or convulsions that do not result in hospitalization, or development of drug dependency or drug abuse.

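### Sections 8.4 and 8.4.6 exempt all progression of the study cancer from AE/SAE reporting, but 10.3.2 makes it reportable after hospitalization or death, so it can enter all-cause SAE and fatal-AE counts

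*Combined protocol and SAP*

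**What the plan says.** Three places in the current text tell sites how to treat progression of the study cancer.

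- Section 8.4: "Progression of the cancer under study is not considered an AE as described in Section 8.4.6 and Appendix 3". It cites both places as if they agree.
- Section 8.4.6 sets the exemption: "Efficacy endpoints as outlined in this section will not be reported to the Sponsor as described in Section 8.4.1". On its scope it adds that "the suspected/actual events covered in this exception include any event that is disease progression of the cancer under study". Neither hospitalization nor death is mentioned.
- Section 10.3.2 (Appendix 3), in the list of events that do meet the AE definition: "Progression of the cancer under study is not considered a reportable event unless it results in hospitalization or death". The next sentence points to Section 8.4.6 for more detail.

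Two further rules bear on the consequence. Section 10.3.3 says "If an event is not an AE per definition above, then it cannot be an SAE even if serious conditions are met". Section 8.4.6 provides a review step: "Any suspected endpoint that upon review is not progression of the cancer under study will be forwarded to Global Pharmacovigilance as an SAE".

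On the analysis side, Section 9.4.2 lists the safety parameters as "including AEs, SAEs, fatal AEs, laboratory tests, and vital signs", and Section 9.6.2 sets out the tiered summaries. The readable parts of Sections 9.4.2, 9.5.2 and 9.6.2 contain no rule for progression terms that have been recorded as AEs.

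**The concern.** The same event is classified in opposite ways. A hospitalization or death caused by progression is a reportable event under 10.3.2, and it then meets the death or hospitalization criterion for an SAE in 10.3.3. Under 8.4 and 8.4.6 it is not an AE, and so by 10.3.3 it cannot be an SAE.

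Safety relative to pembrolizumab is a secondary objective in both cohorts, and Section 2.3 names the assessment of AE and SAE rates as a goal of the study. If a combination works, progression is less frequent in that arm. Counting progression as an SAE or fatal AE then adds events to the less effective arm for a reason that has nothing to do with toxicity, and could offset part of a real excess of toxicity in the other arm. The trial is open-label, so differences in site practice need not balance across arms.

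**Working it through.** **Which rule governs.** Set side by side:

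| Event | 8.4 and 8.4.6 | 10.3.2 with 10.3.3 |
|---|---|---|
| Progression, no hospitalization or death | Not reported | Not reported |
| Progression leading to hospitalization | Not an AE, so not an SAE | Reportable, meets an SAE criterion |
| Progression leading to death | Not an AE, so not an SAE | Reportable, meets an SAE criterion |

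The rules agree on the first row and conflict on the other two. The pointer from 10.3.2 to 8.4.6 does not settle this, because 8.4.6 is silent on hospitalization and death and neither section claims precedence. The review step in 8.4.6 works in one direction: it adds events found not to be progression. No stated step takes out true progression already entered as an SAE.

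**Scale.** The plan gives no figure to reproduce. The inputs are:

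- Early progression on control, 40%: Section 2.1, for first-line pembrolizumab within 4 months.
- Early progression on a combination, 25%: an assumption.
- Share *s* of those progressions leading to hospitalization or death inside the SAE window: an assumption, varied from 5% to 30%. Section 8.4.1 sets the window: "All AEs meeting serious criteria, from the time of intervention allocation through 90 days after cessation of study intervention". It closes at 30 days if new anticancer therapy starts earlier, which is plausible after progression.

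Progression-coded SAEs are 0.40 × *s* on control and 0.25 × *s* on the combination. The artefact is (0.40 − 0.25) × *s* = 0.15 × *s*.

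| *s* | Control (%) | Combination (%) | Artefact (points), all sites follow 10.3.2 | Artefact (points), sites with half the participants do |
|---|---|---|---|---|
| 5% | 2.0 | 1.25 | 0.75 | 0.375 |
| 10% | 4.0 | 2.5 | 1.5 | 0.75 |
| 20% | 8.0 | 5.0 | 3.0 | 1.5 |
| 30% | 12.0 | 7.5 | 4.5 | 2.25 |

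The last column assumes that participants at the two kinds of site have the same outcomes and arm balance.

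Section 9.6.2 gives between-arm intervals for SAEs reaching 5% in one treatment group. Progression alone would reach this on control when 0.40 × *s* = 0.05, that is at *s* = 0.05 / 0.40 = 12.5%, if it were coded under one term and every site followed 10.3.2.

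For these inputs the figures are upper limits, since a participant who already has another SAE adds nothing to the overall SAE proportion. They cover early progression only. The 40% is a first-line figure and should not be carried over to Cohort A.

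**The case against.** The case for leaving this alone has four parts.

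1. *The cross-reference.* A careful site reading 10.3.2 is sent to 8.4.6 and may apply the full exemption. This stands in part. A reader might infer that the SAE and fatal-AE rates will mix progression with toxicity. The documents support only that they can, where sites apply the 10.3.2 exception.

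2. *The summaries already separate much of it.* Section 9.6.2 reports drug-related AEs, drug-related serious AEs and drug-related Grade 3 to 5 AEs as their own categories, and progression not judged drug-related stays out of them. AEs are also analysed by specific term, so progression entries could be seen. The overall serious-AE category is Tier 3, with point estimates only, and the Tier 2 intervals are stated to be descriptive. All of this stands. A reader might infer that a toxic combination would pass as safe. That goes too far, because the distortion is confined mainly to all-cause SAE and fatal-AE counts.

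3. *The analysis rule may exist out of sight.* The Tier 1 text and Table 12 are redacted, the list under the heading for events that do not meet the AE definition is absent from the available text, and a supplemental SAP is foreseen. So it cannot be said that the plan has no exclusion rule, only that none is readable. Even if one exists, the two instructions to sites still conflict.

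4. *The size is not known.* Only the 40% comes from the documents. A reader might divide 320 participants by 7 arms to turn percentages into counts. The documents do not support this: cohort sizes are redacted and one arm closed to enrollment early.

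**Conclusion.** The conflict is real, lies in current text, and does not depend on any redacted passage. Its effect is conditional: progression enters the all-cause SAE and fatal-AE counts only where sites follow 10.3.2. Drug-related categories and the primary endpoint, ORR by BICR, are largely unaffected.

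On the assumptions shown, the artefact is at most about 0.75 to 4.5 percentage points in favour of the arm with less progression. It falls as fewer sites apply 10.3.2 and as more affected participants already have another SAE. With equal early progression in both arms and even site practice it is zero. The upper end needs a 30% share and every site following 10.3.2, so it should not be read as the expected value. The point is worth correcting because two stated rules cannot both be followed and the remedy is small.

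**What to change.** **Reporting.** Reconcile Sections 8.4, 8.4.6 and 10.3.2 to one rule for progression that leads to hospitalization or death, and make the cross-references agree. Keep the 8.4.6 step that forwards events found on review not to be progression. In an open-label trial that step guards against toxicity being put down to the cancer.

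**Analysis.** In Section 9.6.2, state that terms denoting progression of the study cancer and not judged drug-related are excluded from the AE, SAE and fatal-AE summaries and tabulated separately by arm. Events already entered stay in the database, so no safety record is lost. This sentence protects the comparison whichever reporting rule the sponsor adopts.

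**Cost.** Aligned wording in three sections, one sentence in the SAP, one additional table or listing, and a reminder to sites.

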10.3.3 Definition of SAE

If an event is not an AE per definition above, then it cannot be an SAE even if serious conditions are met.

An SAE is defined as any untoward medical occurrence that, at any dose:

- a. Results in death
- b. Is life-threatening
 - The term “life-threatening” in the definition of “serious” refers to an event in which the participant was at risk of death at the time of the event. It does not refer to an event, which hypothetically might have caused death, if it were more severe.
- c. Requires inpatient hospitalization or prolongation of existing hospitalization
 - Hospitalization is defined as an inpatient admission, regardless of length of stay, even if the hospitalization is a precautionary measure for continued observation. (Note: Hospitalization for an elective procedure to treat a preexisting condition that has not

worsened is not an SAE.) A preexisting condition is a clinical condition that is diagnosed prior to the use of an MSD product and is documented in the participant's medical history.

- d. Results in persistent or significant disability/incapacity
 - The term disability means a substantial disruption of a person's ability to conduct normal life functions.
 - This definition is not intended to include experiences of relatively minor medical significance such as uncomplicated headache, nausea, vomiting, diarrhea, influenza, and accidental trauma (eg, sprained ankle) that may interfere with or prevent everyday life functions but do not constitute a substantial disruption.
- e. Is a congenital anomaly/birth defect
 - In offspring of participant taking the product regardless of time to diagnosis.
- f. Other important medical events
 - Medical or scientific judgment should be exercised in deciding whether SAE reporting is appropriate in other situations such as important medical events that may not be immediately life-threatening or result in death or hospitalization but may jeopardize the participant or may require medical or surgical intervention to prevent 1 of the other outcomes listed in the above definition. These events should usually be considered serious.
 - Examples of such events include invasive or malignant cancers, intensive treatment in an emergency room or at home for allergic bronchospasm, blood dyscrasias, or convulsions that do not result in hospitalization, or development of drug dependency or drug abuse.
 - All potential DILI events meeting biochemical criteria of Hy's Law will be reported to the Sponsor, regardless of suspected etiology, as an ECI and SAE with OME criteria in the absence of other SAE criteria within 24 hours of learning of the event.

